10.6.1.4 Follow-up evaluation

Potential drug-induced liver injury events require follow-up monitoring as described in [Table 10–3](#). Monitoring should continue until liver chemistry values normalize, stabilize, or return to Baseline. Determination of stabilization is at the discretion of the investigator in consultation with the hepatologist (as applicable) and UCB responsible physician, as needed.

10.7 Pregnancy testing

Females of childbearing potential will have serum and urine pregnancy tests performed during the study according to the tabular schedules of study assessments (Section 5.2).

10.8 Other safety measurements

10.8.1 Physical examination

Physical examinations will be performed according to the tabular schedules of study procedures (Section 5.2) by a medically qualified clinician licensed to perform the examination. Clinically significant physical examination findings are to be reported as AEs.

10.8.1.1 Complete physical examination

The complete physical examination will include cardiac and respiratory function via auscultation, temperature, and review of all body systems. Genitourinary and breast examinations will be performed for the assessment of Tanner Stage only.

10.8.1.2 Brief physical examination

The brief physical examination will include review of the following body systems:

- Cardiovascular
- Pulmonary
- Abdominal (hepato-gastrointestinal)
- Dermatologic

10.8.2 Neurological examination

Neurological examinations will be performed according to the tabular schedules of study procedures (Section 5.2) by a medically qualified clinician with documented training in the conduct of neurological examinations. If possible, the same clinician should conduct all neurological examinations for the same subject during the study. The investigator or subinvestigator is responsible for confirming the diagnosis of partial-onset seizures.

10.8.2.1 Complete neurological examination

The complete neurological examination will include selected assessment of general neurological status (level of consciousness, mental status, speech), cranial nerves, reflexes, motor system (general motor status, muscle strength, muscle tone), coordination/cerebellar function, and sensation.

The head circumference will be measured according to the tabular schedules of study procedures (Section 5.2).

10.8.2.2 Brief neurological examination

The brief neurological examination will include selected assessment of general neurological status (level of consciousness, mental status, speech), reflexes, muscle strength, and coordination/cerebellar function.

10.8.3 Tanner Stage

The investigator or qualified designee will evaluate the subject's sexual development using the 3-item Tanner scale, according to the tabular schedules of study procedures (Section 5.2). The investigator should use clinical judgment in deciding which subjects are selected for evaluation of Tanner Stage (ie, those subjects who are pubescent at Visit 1 or who enter puberty during the course of the study).

10.8.4 12-lead ECG

Standard 12-lead ECGs will be performed according to the tabular schedules of study assessments (Section 5.2). Two interpretable recordings should be made approximately 20 to 30 minutes apart. Care should be taken to ensure proper lead placement and quality ECG recordings. The ECGs will be performed prior to any blood draws and vital signs assessment.

Subjects should rest in a supine position approximately 5 minutes prior to each recording and during the recording.

All subjects will be required to have a 12-lead ECG (2 interpretable recordings approximately 20 to 30 minutes apart) conducted at LCM C_{max} 1 week after a LCM dose increase to ≥ 8 mg/kg/day, after subsequent dose increases (ie, the first time a subject reaches a LCM dose of 8mg/kg/day, 9mg/kg/day, 10mg/kg/day, etc) or for LCM doses of ≥ 400 mg/day (ie, the first time a subject reaches a LCM dose of 400mg/day, 500mg/day, etc), or when a new concomitant AED is introduced during the study. This ECG can be conducted at an Unscheduled Visit, if necessary. Subjects having a LCM dose increase to ≥ 8 mg/kg/day or to ≥ 400 mg/day, or when a new concomitant AED is added will be required to arrive at the clinic prior to taking their morning dose of LCM. Subjects will be administered their morning LCM dose by study personnel at the clinic so that an ECG (2 interpretable recordings approximately 20 to 30 minutes apart prior to any blood sample collection or vital signs assessment) can be performed 30 minutes to 1 hour after the administration of LCM.

10.8.4.1 Overall ECG interpretation

Electrocardiograms will be reviewed locally by the investigator, subinvestigator, or qualified designated reader and at a central ECG laboratory. If the reading identifies second or third degree AV block or another abnormal ECG finding that is assessed by the investigator to be clinically significant, then the ECG should be repeated on the same day. If the clinically significant abnormality is confirmed by the repeat ECG, then the subject must be withdrawn from the study (see Section 6.3). The investigator may consult with the cardiologist at the central ECG laboratory to confirm the presence of a clinically significant ECG abnormality. It remains the responsibility of the investigator to decide whether an ECG finding is of clinical significance on the basis of the complete clinical picture and whether this finding influences the subject's participation in the study.

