6.3 Withdrawal criteria

Subjects are free to withdraw or the subject's legal representatives are free to withdraw the subject from the study at any time, without prejudice to their continued care.

Participation in this study **must** be discontinued for any of the following reasons:

1. Subject experiences intolerable AEs, including clinically relevant abnormal laboratory findings that, in the opinion of the investigator, preclude further participation in the study.
2. The sponsor or a regulatory agency requests withdrawal of the subject.
3. Subject has a QTc interval ≥ 500 ms that is confirmed by a cardiologist over read on any ECG.
4. Subject develops a second-degree atrioventricular (AV) block while awake or develops a third-degree AV block.
5. For subjects ≥ 6 years of age, subject has actual suicidal ideation since last visit as indicated by a positive response ("Yes") to either Question 4 or Question 5 of the C-SSRS. The subject should be referred immediately to a Mental Healthcare Professional and must be withdrawn from the study.
6. Subject is unwilling or unable to continue or legal representative is unwilling or unable to allow the subject to continue in the study.
7. Investigator decides that withdrawal from further participation would be in the subject's best interest.
9. Female subject who achieves menarche during the study and does not practice contraception as provided in Exclusion Criteria 5 unless sexually abstinent.

10. Subject becomes pregnant, as evidenced by a positive pregnancy test.

Participation in this study **may** be discontinued for any of the following reasons:

1. Any clinically relevant change in medical or psychiatric condition (if, in the opinion of the investigator, the condition warrants discontinuation from the study).
2. Subject requires a medication that is not permitted by the protocol (see Section 7.8.1).
3. Subject and/or legal representative is noncompliant with study procedures or medication, in the opinion of the investigator.

Subjects discontinuing LCM for any reason should taper off medication as described in Section 7.2.2. Whenever possible, these cases should be discussed with the Medical Monitor prior to withdrawing the subject from the study.

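### Protocol Sections 6.3 and 10.8.4.1 state different mandatory withdrawal rules for AV block and other ECG findings, and need to be reconciled

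*Protocol*

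**What the plan says.** Protocol Section 6.3 opens its mandatory list with "Participation in this study must be discontinued for any of the following reasons". Criterion 4 of that list is "Subject develops a second-degree atrioventricular (AV) block while awake or develops a third-degree AV block". No repeat or second reading is attached to it. Criterion 3, directly above, covers a QTc interval of 500 ms or more and does carry a check: the value counts when it is one "that is confirmed by a cardiologist over read on any ECG".

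Protocol Section 10.8.4.1 describes what happens when an ECG is read. The trigger is: "If the reading identifies second or third degree AV block or another abnormal ECG finding that is assessed by the investigator to be clinically significant". The next step is "then the ECG should be repeated on the same day". Then comes the withdrawal rule: "If the clinically significant abnormality is confirmed by the repeat ECG, then the subject must be withdrawn from the study", with a reference to Section 6.3. The paragraph closes by giving the investigator two decisions. One is clinical significance: "It remains the responsibility of the investigator to decide whether an ECG finding is of clinical significance on the basis of the complete clinical picture". The other, in the same sentence, is "whether this finding influences the subject's participation in the study".

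Section 6.3 does not refer back to Section 10.8.4.1. The protocol amendment logs supplied show no change to either rule.

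**The concern.** Both passages use mandatory language for the same kind of event, but they differ on four things: whether a repeat ECG plays a part, whether the subject must be awake for second-degree block to count, which other ECG findings oblige withdrawal, and how much is left to the investigator.

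Two outputs depend on who is withdrawn. The incidence of TEAEs leading to study discontinuation is one of three primary safety variables (Protocol Section 4.1.1, SAP Section 2.2.1). It is tabulated overall, by weight band, by enrollment group and by 3-month interval (SAP Section 8.2). Withdrawal criteria are also one of the protocol deviation categories in SAP Section 3.4, which wants deviation rules programmed as algorithms whenever possible. An algorithm written from criterion 4 and one written from Section 10.8.4.1 would flag different subjects.

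**Working it through.** The plan gives no figure to reproduce and no arithmetic applies. The check sets the two texts side by side and runs the same cases through both.

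| Element | Section 6.3, criterion 4 | Section 10.8.4.1 |
|---|---|---|
| Second-degree AV block | Only if awake | No waking condition |
| Third-degree AV block | Any | Any |
| Repeat ECG | Not mentioned | Same day |
| Mandatory withdrawal stated when | The block develops | The repeat confirms the abnormality |
| Other ECG findings | Not covered here; QTc is in criterion 3 | Any that is clinically significant and confirmed |
| Investigator discretion | None within the criterion | Significance, and whether participation is affected |

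Case 1: second-degree block while awake, or any third-degree block, on the first tracing but absent on the repeat. Criterion 4 requires withdrawal. The withdrawal condition in Section 10.8.4.1 is not met, and that section does not say what follows.

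Case 2: second-degree block in a sleeping subject, judged clinically significant and present again on the repeat. Criterion 4 is not met. Section 10.8.4.1 requires withdrawal.

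Case 3: a clinically significant finding that is neither AV block nor a QTc of 500 ms or more, confirmed on the repeat. Section 10.8.4.1 requires withdrawal and points to Section 6.3. The only ECG-specific items there are criteria 3 and 4. What remains is general: criterion 1 (intolerable AEs that in the investigator's opinion preclude participation) and criterion 7 (the investigator decides that withdrawal is in the subject's best interest). Both rest on judgement and do not supply the automatic rule that Section 10.8.4.1 attributes to Section 6.3.

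Case 4: a confirmed block judged clinically significant, where the investigator concludes that it need not affect participation. Within Section 10.8.4.1 itself, the withdrawal sentence requires withdrawal and the closing sentence appears to leave the matter open.

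The texts diverge in cases 1 to 3. In case 4, Section 10.8.4.1 is at odds with itself.

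**The case against.** The strongest reply is that Section 10.8.4.1 states a sufficient condition. It says that a confirmed abnormality leads to withdrawal; it does not say that an unconfirmed one allows the subject to stay, and it does not waive criterion 4. A site that withdraws whenever either passage is triggered obeys both mandatory rules. This stands, and it rules out two stronger readings that a reader might infer. One is that Section 10.8.4.1 allows withdrawal only after confirmation; the text does not say so. The other is that two sites could handle the same ECG differently and both comply with the protocol. A site that keeps a case 1 subject does not satisfy criterion 4 as written, whatever the repeat shows.

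A related reply is that Section 10.8.4.1 is the working procedure for establishing criterion 4, with the repeat showing whether the block has truly developed. That softens case 1. However, Section 6.3 does not point to any such procedure, and criterion 3 shows that the list states a confirmation step where one is intended. Nor does this reading explain the missing waking condition, the extension to other findings, or the closing discretion sentence.

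It is also fair to say that sleeping second-degree block is not exempted by Section 6.3. Criterion 4 simply does not list it, and criterion 7 remains available.

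Finally, the safety signal does not depend on withdrawal. Second- and third-degree AV block are AEs of special interest, reported immediately (Protocol Sections 10.3 and 10.4), and other significant TEAEs in SAP Appendix 12.2. All analyses are descriptive, without hypothesis testing (Protocol Section 12.2). This stands too: the exposure is limited to the discontinuation count and the deviation classification.

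**Conclusion.** The point holds as an inconsistency between stated mandatory rules. The two passages differ on confirmation, on the waking condition and on which other ECG findings oblige withdrawal, and the discretion sentence sits uneasily with the mandatory one before it. The decision on a given ECG can depend on which passage a site follows. That can change who is withdrawn, the count for one primary safety variable, and what is recorded as a withdrawal-criteria deviation.

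The number of subjects affected cannot be estimated and may be small. A reader might be tempted to put a percentage on case 1 by assuming how often a block reappears on a same-day repeat. The documents give neither that probability nor an expected number of AV block events, so any such figure would only restate the assumption.

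The conclusion rests on the current wording of the two sections. It takes no position on which rule is clinically right.

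**What to change.** Reconcile criterion 4 of Section 6.3 with Section 10.8.4.1 so that a single text states:

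- whether confirmation by a repeat ECG applies to AV block;
- whether the waking condition applies to second-degree block;
- which other ECG findings, if any, are mandatory reasons for withdrawal, with a matching item in Section 6.3;
- how the investigator's discretion fits with the mandatory wording.

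Cross-reference the two sections in both directions. The sponsor's clinical team decides the content.

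For ECGs already collected, the separate important protocol deviations document described in SAP Section 3.4 should record which text was applied when withdrawal-criteria deviations were classified.

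The cost is protocol wording and one entry in the deviations document. No new procedure, visit or data collection is needed.

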10.8.5 Vital signs, body weight, and height

Noninvasive blood pressure (systolic and diastolic) and pulse rate will be measured at clinic visits after at least 3 minutes at rest in a supine position, according to the tabular schedules of study procedures (Section 5.2). Assessment of orthostatic changes (only in ambulatory subjects) will be as follows: after the 3-minute measurement with the subject in a supine position, the subject will be asked to stand up, and blood pressure and pulse rate will be taken 1 minute and 3 minutes after standing up, as feasible.

Body weight will be determined without shoes and wearing light clothing, and height will be measured without shoes. Body weight and height will be assessed according to the tabular schedules of study procedures (Section 5.2).

10.8.6 Assessment of suicidality

Suicidality will be assessed by trained study personnel using the C-SSRS (Columbia University Medical Center, 2008). This scale will be used for subject's eligibility for the study as well as to assess suicidal ideation and behavior that may occur during the study.

The C-SSRS will be completed according to the tabular schedules of study procedures (Section 5.2). This scale will be completed for subjects ≥ 6 years of age. The "Since Last Visit" version of the C-SSRS should be used. If a subject becomes 6 years of age during the study, the

“Already Enrolled” version of the C-SSRS should be used at the first visit at which the subject is 6 years of age and the “Since Last Visit” version at subsequent visits.

The C-SSRS is not validated for subjects <6 years of age and will not be used for this population. Subjects should be monitored for any changes in mood, ideas, or behavior for warning signs of depression. The investigator should be aware of common warning signs that might be a signal for risk of depression. For common signs and symptoms of depression in children younger than 6 years old, reference should be made to the current version of the Diagnostic and Statistical Manual of Mental Disorders. Parents and caregivers should also be advised accordingly and effort should be made at clinic visits to specifically assess potential depression.

10.8.7 Achenbach CBCL

The Achenbach CBCL is a widely used validated questionnaire to evaluate a child’s competencies and behavioral/emotional problems. Behavioral problems will be scored by the parent(s)/legal representative(s).

Depending on the subject’s age, 2 versions of the Achenbach CBCL will be used. The CBCL/1½-5 checklist is intended for use in children 18 months to 5 years and 11 months of age (Achenbach and Rescorla, 2000). For subjects ≥6 years to <17 years of age, the CBCL/6-18 version will be used (Achenbach and Rescorla, 2001). The version of the Achenbach CBCL appropriate to each subject’s age should be administered with the following exception: For subjects who completed the CBCL/1½-5 at the Baseline assessment of the previous study and turn 6 years of age within 1 year after the Baseline assessment of the primary study, the CBCL/1½-5 should be completed for 1 year after the Baseline assessment of the primary study, and subsequently the CBCL/6-18 should be completed. The Achenbach CBCL will only be administered in countries where a validated translated version is available.

The Achenbach CBCL will be completed according to the tabular schedules of study procedures (Section 5.2). The completion of the Achenbach CBCL will require approximately 45 minutes.

In both questionnaires, the occurrence of certain problems and behaviors in the past 6 months will be scored on the following scale:

- 0=not true (as far as known)
- 1=somewhat or sometimes true
- 2=very true or often true

Eight syndrome scores will be calculated from these questions, which will in turn be summarized by 2 composite scores. Additionally, for each score on the question, syndrome, and total level, categorizations based on a normative sample will be used to evaluate normal, borderline, or clinically relevant behavior.

In addition, the CBCL/6-18 includes ratings related to performance in school, activities in leisure time, and special interests.

10.8.8 BRIEF-P and BRIEF

The BRIEF-P and the BRIEF are validated tools that will be used for the evaluation of subjects ≥2 years to <5 years of age and ≥5 years of age, respectively (Gioia et al, 2000). The BRIEF-P or BRIEF appropriate for each subject’s age should be completed, with the following exception:

For subjects who completed the BRIEF-P at the Baseline assessment of the previous study and turn 5 years of age within 1 year after the Baseline assessment of the primary study, the BRIEF-P should be completed for 1 year after the Baseline assessment of the primary study, and subsequently the BRIEF should be completed. The BRIEF-P and BRIEF will be administered according to the tabular schedules of study procedures (Section 5.2). The BRIEF-P and BRIEF will only be administered in countries where a validated translated version is available.

The BRIEF-P and BRIEF include rating forms used by parents to assess subjects' executive functioning. Executive functions broadly encompass a set of cognitive skills that are responsible for the planning, initiation, sequencing, and monitoring of complex goal-directed behavior. The BRIEF-P rating form consists of items that measure various aspects of executive functioning: Inhibit, Shift, Emotional Control, Working Memory, and Plan/Organize. The clinical scales form 3 broad indexes (Inhibitory Self-Control, Flexibility, and Emergent Metacognition) and 1 composite score (Global Executive Composite).

The BRIEF rating form contains items in nonoverlapping clinical scales. These theoretically and statistically derived scales form 2 broader indexes: Behavioral Regulation (3 scales) and Metacognition (5 scales), as well as a Global Executive Composite score.

Both the BRIEF-P and the BRIEF include validity scales to measure negativity and inconsistency of responses.

10.8.9 Bayley Scales of Infant and Toddler Development, Third Edition

The Bayley-III scales are recognized internationally as one of the most comprehensive developmental assessment instruments (Sattler and Hoge, 2006) used to examine the major facets of a young child's development (Bayley, 2006). The Bayley-III scales are a standardized, individually administered, adaptive assessment that measures the developmental functioning of infants and young pediatric subjects from 1 month to 42 months of age (Bayley, 2006). The Bayley-III scales measure cognitive, language, motor, social-emotional, and adaptive development and are a revision of the predecessor, the Bayley Scales of Infant Development, Second Edition (Bayley, 1993). The Bayley-III scales are a technically sound instrument, with strong internal consistency, as well as test-retest stability. The Bayley-III scales are validated only in English.

This scale is validated as a tool for assessment of neurological development in young pediatric subjects and is therefore considered appropriate for EP0034.

The Bayley-III scales are an individually administered, adaptive assessment that presents pediatric subjects with situations and tasks designed to produce an observable set of behavioral responses. They consist of a cognitive scale, a language composite scale with receptive and expressive language subscales, and a motor composite scale with fine and gross motor subscales to be completed by the investigator or designee. It also has a social emotional scale, comprising social-emotional competence, and sensory processing, and an adaptive behavior scale, which assesses the attainment of skills necessary for the development of independence, to be completed by the child's parent or caregiver.

The completion of the Bayley-III scales will require approximately 50 minutes for pediatric subjects who are 12 months old or younger and 90 minutes for pediatric subjects aged 12 months to 18 months.

The scale will be completed according to the tabular schedules of study procedures (Section 5.2). The same scale should be completed for 1 year after the Baseline assessment of the primary study, even if the subject turns >18 months of age during that period.

